## 1.2 History of Development and Characteristics of ART-123

## 1.2.1 Pharmacological Characteristics of ART-123

Thrombomodulin (TM) is a glycoprotein present on vascular endothelial cells. This physiologic coagulation factor facilitates the regulation of blood coagulation in the body. ART-123 (non-proprietary name: thrombomodulin alfa (recombinant)) is soluble human TM, expressed in animal cells, that consists of only the extracellular domain of poorly soluble natural TM, the extracellular domain containing the active site. ART-123 has a coagulation-regulating effect comparable to natural TM. A drug product containing ART-123 as the active ingredient (proprietary name: Recomodulin® Inj. 12800) was approved in Japan in 2008 for the indication of disseminated intravascular coagulation syndrome. ART-123 appears to have anti-inflammatory actions and protects against vascular endothelial damage .

## 1.2.2 Characteristics of ART-123 (nonclinical)

One mechanism for the onset of neuropathy is thought to be prolongation of the inflammatory response. The supposed anti-inflammatory action of ART-123 was investigated in a rat model of CIPN induced with oxaliplatin. Intraperitoneal administration of 0.3 mg/kg (1,900 U/kg) to 10 mg/kg (65,000 U/kg) of ART-123 given for 7 days suppressed escape behavior in response to mechanical hyperalgesia in a dose-dependent manner. ART-123 did not suppress the growth-inhibiting effect of oxaliplatin on cancer cells in a cultured human cancer cell line. These findings suggest that ART-123 may prevent the onset of oxaliplatin-induced peripheral neuropathy without affecting the anti-tumor activity of oxaliplatin.

# 2. Study Objectives

To assess, under placebo-controlled conditions, the efficacy and safety of ART-123 for preventing the onset of oxaliplatin-induced peripheral neuropathy in postoperative adjuvant chemotherapy that includes oxaliplatin in patients with pStage II or III colon cancer after radical resection (R0 surgery)

## 3. Study Population

Patients with pStage II or III colon cancer after radical resection (R0 surgery)

#### 3.1 Inclusion Criteria

Patients who meet all of the following criteria are eligible:

- [1] Age 20 years or older but not older than 79 years at the time of informed consent
- [2] Male or female
- [3] Inpatient or outpatient
- [4] Patients with histologically diagnosed colon cancer (or rectosigmoid cancer) at pStage II, IIIa, or IIIb based on "Japanese Classification of Colorectal Carcinoma (Eighth Edition)" 
- [5] Deemed to have undergone curative A (Cur A) surgery
- [6] ECOG performance status of 0 or 1 on the day of registration
- [7] The most recent laboratory findings from 7 days to 1 day before registration meet all of the following criteria:

• White blood cell count  $>3,500/\text{mm}^3$  and  $<100,000/\text{mm}^3$ 

Neutrophil count >1,500/mm³
 Platelet count >100,000/mm³
 Haemoglobin >9.0 g/dL
 Total bilirubin <2.0 mg/dL

 $\bullet$  Serum creatinine  $$\operatorname{not}$$  not more than the upper limit of the normal range and not more than 2 mg/dL

- AST (GOT) and ALT (GPT) not more than 2.5-fold the upper limit of the normal range and not more than 100 IU/L
- [8] Scheduled as of the time of registration to undergo 12 courses of postoperative adjuvant chemotherapy with mFOLFOX6
- [9] Able to sufficiently understand the clinical study and give informed consent

## 3.2 Exclusion Criteria

The presence of any of the following at the time of registration will exclude the patient from this study:

- [1] History of hypersensitivity to any of the ingredients in thrombomodulin alfa (recombinant)
- [2] Peripheral neuropathy or central nervous system (CNS) damage
- [3] Mental disorder of a severity that would affect the efficacy and safety evaluations in this study
- [4] Any treatment history of systemic chemotherapy (including any drug in the clinical trial stage) or radiotherapy intended to provide an anti-tumor effect
- [5] Active double cancer\*1
  - \*1 Synchronous double cancer or metachronous double cancer with disease-free period of no more than 5 years; does not include lesions equivalent to carcinoma in situ or intramucosal carcinoma deemed to have resolved with local treatment
- [6] Yet to recover from an operation or a complication such as a postoperative infection
- [7] Serious intestinal obstruction, diarrhoea, or pyrexia

- [8] History of cerebrovascular disorder (e.g., cerebral haemorrhage, cerebral infarction) within 52 weeks (364 days) before informed consent
- [9] Intracranial haemorrhage, pulmonary haemorrhage, or gastrointestinal haemorrhage (persistent haematemesis/blood in stool or gastrointestinal ulcer-induced haemorrhage)
- [10] Unconfirmed completion of a haemostasis procedure after CNS surgery or after trauma
- [11] Receiving transfusion, a blood derivative, G-CSF, or another hematopoietic factor within 7 days before the laboratory tests performed to assess registration eligibility
- [12] Hepatitis B infection and a positive test result for HBs antigen. Patients negative for HBs antigen but positive for HBc or HBs antibody must undergo an HBV-DNA test. A result at or above the normal range will disqualify the patient from enrollment. Test data obtained within 6 months before registration may be used.
- [13] A positive test result for HIV antigen or antibody
- [14] Establishment of an artificial anus (even if temporary) in colorectal cancer surgery
- [15] Administration of another investigational product within 16 weeks (112 days) before informed consent or undergoing observation that is still ongoing a day before informed consent
- [16] Pregnancy or possible pregnancy; wish to become pregnant during the study period; breastfeeding
- [17] Having participated in this study in the past
- [18] Prior treatment history with thrombomodulin alfa (recombinant)
- [19] Is otherwise found unsuited for the study by the investigator or subinvestigator

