## 6.2 Investigational Product Dosage Form and Strength

- [1] Investigational medicinal product
  - Injection
  - A freeze-dried formulation containing 12,800 U thrombomodulin alfa (recombinant) per vial
  - Contains 40 mg L-arginine hydrochloride and a pH adjuster as excipients
- [2] Control drug
  - Injection
  - A freeze-dried formulation free of thrombomodulin alfa (recombinant) that is indistinguishable in appearance from ART-123 (the investigational medicinal product)
  - Contains 29 mg L-arginine hydrochloride, 800.1 mg Polysorbate, 1.5 mg sodium chloride, and a pH adjuster as excipients

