## 7.2.3 Assigning Subjects to Treatment Groups

Subjects will be assigned to treatment groups after IWRS entry.

The subject registration center will confirm subject eligibility and then assign each subject to the ART-123 3-dose group, ART-123 1-dose group, or placebo group. Block randomization with the study sites as a stratification factor will be used to achieve an ART-123 3-dose group, ART-123 1-dose group, and placebo group assignment ratio of 1:1:1.

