# 8. Subject Treatment

# 8.1 Investigational Product Dosage and Administration

# 8.1.1 Dosage and Administration

Administer the investigational product (ART-123 380 U/kg or placebo) once daily by intravenous infusion over approximately 30 minutes from Days 1 to 3 of each course of postoperative adjuvant chemotherapy (mFOLFOX6).

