# [1] ART-123 3-dose group

On Day 1, initiate ART-123 administration from 2 hours to 30 minutes before oxaliplatin administration and complete administration before the start of oxaliplatin administration. On Days 2 and 3, administer ART-123 at about the same time as on Day 1 whenever possible.

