# [2] ART-123 1-dose group

On Day 1, initiate ART-123 administration from 2 hours to 30 minutes before oxaliplatin administration and complete administration before the start of oxaliplatin administration. On Days 2 and 3, administer the placebo at about the same time as on Day 1 whenever possible.

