#### [3] Placebo group

On Day 1, initiate placebo administration from 2 hours to 30 minutes before oxaliplatin administration and complete administration before the start of oxaliplatin administration. On Days 2 and 3, administer the placebo at about the same time as on Day 1 whenever possible.

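### Exclusion [1] screens only for hypersensitivity to the active product's ingredients, yet section 6.2 lists Polysorbate for the placebo alone, so no specific criterion covers it

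*Protocol*

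**What the plan says.** Protocol section 3.2, exclusion [1], and the matching synopsis entry exclude patients with "History of hypersensitivity to any of the ingredients in thrombomodulin alfa (recombinant"). Section 3.3.2 gives subject safety as the reason for this criterion.

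Section 6.2 describes the two products separately. For ART-123: "Contains 40 mg L-arginine hydrochloride and a pH adjuster as excipients". For the placebo: "Contains 29 mg L-arginine hydrochloride, 800.1 mg Polysorbate, 1.5 mg sodium chloride, and a pH adjuster as excipients".

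Section 8.1.1 sets out who receives which product. All infusions are given "once daily by intravenous infusion over approximately 30 minutes from Days 1 to 3 of each course".
- 3-dose group: ART-123 throughout; after the Day 1 dose, "On Days 2 and 3, administer ART-123 at about the same time as on Day 1 whenever possible".
- 1-dose group: ART-123 on Day 1, then "On Days 2 and 3, administer the placebo at about the same time as on Day 1 whenever possible".
- Placebo group: placebo on all three days, starting with "On Day 1, initiate placebo administration from 2 hours to 30 minutes before oxaliplatin administration".

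Section 7.2.3 fixes equal allocation to the three groups, and section 12.1 plans 25 subjects in each.

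Two general provisions also bear on entry. Exclusion [19] lets the investigator exclude anyone otherwise considered unsuitable, and section 3.3.2 explains that this includes cases where safety cannot be guaranteed. Section 10.1 tells the investigator not to enrol a patient whose safety cannot be ensured.

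**The concern.** In a randomised, blinded trial, nobody at the site knows at entry which product a patient will be given. Every candidate therefore has to be fit to receive either product. Exclusion [1] applies an ingredient-based allergy check to only one of the two, and the other contains a listed ingredient that the first does not.

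A site that works through the criteria as written is asked about hypersensitivity to the ingredients of thrombomodulin alfa (recombinant) and to nothing else. A patient who reports a past reaction to Polysorbate meets no specific exclusion. If that patient enters and is allocated to the placebo or 1-dose group, the ingredient is infused intravenously, repeatedly, from a product that offers the patient no expected benefit. The stated purpose of [1], subject safety, applies to the placebo as much as to ART-123.

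**Working it through.** **1. Compare the excipient lists in section 6.2.**

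| Excipient | ART-123 | Placebo |
|---|---|---|
| L-arginine hydrochloride | listed (40 mg) | listed (29 mg) |
| pH adjuster | listed | listed |
| Sodium chloride | not listed | listed (1.5 mg) |
| Polysorbate | not listed | listed |

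Two excipients appear for the placebo only. Sodium chloride raises no separate question, because section 8.1.3 allows physiological saline as the diluent for either product. That leaves Polysorbate. The quantity printed for it may be an artefact of text extraction and is not relied on. The point rests on the ingredient being listed, and [1] sets no quantity threshold.

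**2. Set the lists against exclusion [1].** The criterion can be read narrowly, as the active substance, or broadly, as the formulated ART-123 product. On either reading Polysorbate falls outside it.

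**3. Check the other criteria.** Exclusions [2] to [18] concern existing disease, prior treatment, infection, surgery, pregnancy and previous participation. None concerns allergy. Exclusion [19] and section 10.1 are general; neither names an ingredient or an allergy. The eligibility confirmation entered in the IWRS (section 7.2.1, item [4]) follows the listed criteria and so asks nothing further.

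**4. Count planned placebo exposure.** The plan's own total in section 8.1.2 reproduces: 3 infusions per course × 12 courses = 36 per subject. Splitting these by product:
- placebo group: 3 × 12 = 36 placebo infusions per subject
- 1-dose group: 2 × 12 = 24 placebo infusions per subject
- 3-dose group: 0 × 12 = 0

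Subjects planned to receive any placebo: 2 groups × 25 = 50 of 75. At 1:1:1 allocation, any one enrolled patient has a 2/3 chance of placebo exposure.

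**5. What these counts do and do not measure.** They show how widely the placebo is used. They do not give the expected number of affected patients. Writing q for the proportion of entrants with a known Polysorbate hypersensitivity who are not stopped by [19] or section 10.1, the expected number exposed is 75 × q × 2/3 = 50q. The protocol gives no value for q. It is presumably small, and the conclusion that the wording is incomplete holds for any value.

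The precision argument behind 25 per group plays no part in this check.

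**The case against.** The strongest reply is that the protocol already has the means to keep such a patient out. Exclusion [19] is available, its rationale expressly mentions patient safety, section 10.1 is phrased as an obligation, and section 6.2 discloses the placebo's excipients to the same investigators. A reader might infer from [1] that a patient with a known Polysorbate allergy is eligible and would be infused with it. The documents do not support that: an investigator aware of the allergy can, and under section 10.1 should, decline to enrol the patient, and exposure after enrolment is a two-in-three chance. What remains is that these provisions work only if someone raises the question, and no listed criterion raises it. The sponsor gave ingredient hypersensitivity its own criterion for ART-123, and the same reasoning extends to the placebo.

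It can also be said that sections 3.2 and 6.2 do not contradict each other. That is right: one limits an exclusion and the other lists contents. The fault is incomplete coverage.

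A reader might further infer a monitoring gap, because section 10.2.3 speaks of Recomodulin only. That does not follow. The products are indistinguishable (sections 5.1, 6.2), so a blinded investigator has to observe every infusion, and section 9.7.4.1 counts any adverse event after the investigational product as treatment-emergent.

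Nor do the documents support a claim that a hypersensitivity analysis would be distorted. Section 12.7.1 tabulates adverse events by name and group and specifies no dedicated hypersensitivity comparison.

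**Conclusion.** The point holds in limited form. Exclusion [1] covers the ingredients of one of the two products that a randomised patient may receive, and Polysorbate is listed only for the other. No specific criterion excludes a patient with a known hypersensitivity to it; only a discretionary criterion and a general safety rule could.

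The reach is 50 of 75 planned subjects receiving placebo, with 36 or 24 planned placebo infusions each. The likely number of affected patients is small and cannot be estimated from the protocol. The conclusion assumes that the section 6.2 excipient lists are correct as to which ingredients are present. It does not depend on the amounts. The comparison of texts is firm. The practical consequence is an avoidable risk of low probability, worth correcting because the correction is so cheap.

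**What to change.** Reconcile exclusion [1], in both section 3.2 and the synopsis, with section 6.2. Keep the opening of the criterion and replace its closing reference to thrombomodulin alfa (recombinant) with: ART-123 or ART-123 (placebo). Ingredients need not be named one by one, since section 6.2 lists them. Update the eligibility confirmation entered in the IWRS under section 7.2.1 so that sites are asked the same question. Section 10.2.3 needs no change.

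The cost is one line of text in two places and a matching entry in the registration system. At most, an occasional patient is excluded who would otherwise have entered. Sample size, endpoints and analyses are unaffected.

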## 3.3 Rationale for Inclusion and Exclusion Criteria

## 3.3.1 Rationale for Inclusion Criteria

- [1] Subjects must be at least 20 years old to be sufficiently competent to give consent. An upper age limit of 79 years was set out of concern for subject safety.
- [2] The sex of the subjects is not limited because sex is not thought to affect the evaluation of efficacy or safety in the study.
- [3] The hospitalization status of the subjects is not limited because this is not thought to affect the evaluation of efficacy or safety in the study.
- [4] and [5] The study will be in patients with colorectal cancer following radical resection, who have a better prognosis than patients with unresectable, advanced, or recurrent colorectal cancer. The study will be in patients with pStage II or III colon cancer following resection because the Guidelines for the Treatment of Colorectal Cancer, in the section on chemotherapy eligibility, requires Stage II colorectal cancer with a high risk of recurrence or Stage III colorectal cancer for postoperative adjuvant chemotherapy, and patients with Stage II and III colon cancer are indicated for postoperative adjuvant chemotherapy in the package insert of oxaliplatin.
- [6] This criterion was established to select relatively healthy subjects.
- [7] This criterion was established out of concern for subject safety.
- [8] The efficacy of Recomodulin will be investigated on CIPN induced by oxaliplatin, which frequently causes this condition. The oxaliplatin-containing postoperative adjuvant chemotherapy regimens recommended in the Guidelines for the Treatment of Colorectal Cancer are FOLFOX and CapeOX. FOLFOX compliance is readily determinable because the regimen is administered under the control

of healthcare professionals, which makes the regimen ideal for this first study to evaluate the efficacy of Recomodulin in CIPN. The standard FOLFOX regimen mFOLFOX6 was selected. The standard mFOLFOX6 treatment duration of 6 months (12 courses) was selected to allow evaluation of the efficacy of Recomodulin in oxaliplatin-induced chronic neuropathy.

[9] This criterion was established to ensure that the study is ethically consistent.

### 3.3.2 Rationale for Exclusion Criteria

- [1] This criterion was established out of concern for subject safety.
- [2] to [4] These criteria were established because of the possible impact these conditions could have on the efficacy and safety evaluations in the study.
- [5] This criterion was established because of the potential impact on the evaluation of safety.
- [6] and [7] These criteria were established out of concern for subject safety and in reference to the general indications for postoperative adjuvant chemotherapy in the Guidelines for the Treatment of Colorectal Cancer.
- [8] to [10] As these conditions are listed in the Careful Administration and Contraindications sections of the Recomodulin package insert, these criteria were established out of concern for subject safety.
- [11] This criterion was established out of concern for subject safety to prevent the registration of patients satisfying the inclusion criteria because of transfusion or the like.
- [12] This criterion was established out of concern for subject safety because HBV reactivation during or after postoperative adjuvant chemotherapy could lead to hepatitis B onset.
- [13] to [16] These criteria were established out of concern for subject safety.
- [17] and [18] These criteria were established because of the possible impact these conditions could have on the efficacy and safety evaluations in the study.
- [19] This criterion was included to allow exclusion when the evaluation of efficacy and safety in the study could be impacted by another reason and when the investigator or subinvestigator determines that subject safety cannot be guaranteed.

## 4. Subject Informed Consent

## 4.1 Authoring of the Informed Consent Form

Based on the reference informed consent form provided by the sponsor, the investigator will author an informed consent form and submit the document to the sponsor. The informed consent form will contain the statements for patients presented below. The investigator will consult with the sponsor to review the completed informed consent form and then obtain the approval of an institutional review board selected by the director of the study site.

*Information for patients* 

- [1] That the study involves research.
- [2] Purpose of the study.
- [3] The name, title, and contact information of the investigator or subinvestigator.
- [4] Study methodology.
- [5] The expected clinical benefits and risks or inconveniences.
- [6] The alternative treatments that may be available for the disease and their important potential risks and benefits.
- [7] The scheduled duration of study participation by the subjects.
- [8] That participation in the study is voluntary and that the subject may refuse to participate or stop participating in the study at any time. Also that the subject would not be treated disadvantageously for refusing to participate or withdrawing consent and would not lose benefits to which the subject would be otherwise entitled for not participating.
- [9] That the monitor(s), the auditor(s), the institutional review board, and the regulatory authority(ies) will be granted direct access to the subject's treatment-related source documents, without violating the confidentiality of the subject, and that, by signing the written informed consent form, the subject is authorizing such access.
- [10] The privacy of the subject would be maintained if the study results are published.
- [11] The person(s) in the study site to contact for obtaining further information regarding the study and the rights of subjects, and whom to consult or contact in the event of a study-related injury.
- [12] Compensation and treatment to which the subject is entitled if the subject is injured in relation to the study.
- [13] The number of subjects scheduled to participate in the study.
- [14] That the subject will be promptly informed if information becomes available that may be relevant to the subject's willingness to continue participating in the study.
- [15] The foreseeable circumstances and/or reasons under which the subject's participation in the study may be terminated.
- [16] The expenses, if any, required of the subject.
- [17] The monetary and other payments, if any, to the subject for participating in the study.
- [18] Rules with which the subject is expected to comply.
- [19] That any doctor treating the subject will be notified about the participation of the subject in the study.
- [20] The type of institutional review board, that the institutional review board will conduct reviews to determine whether the study should be conducted or continued based on its scientific and ethical

merits, and that the opinions of the institutional review board will be relayed to the director of the study site.

- [21] The name and address of the person installing the institutional review board and how to obtain information about this person.
- [22] That any remaining samples might be used for future research for drug development.
- [23] That data may be used not only for approval review of the drug product but also for cross-sectional studies by the regulatory authorities as well as guideline preparation.
- [24] That data may be used secondarily.
- [25] That data obtained before the subject gives informed consent could be used.

